The trial will be carried out in accordance with International Conference on Harmonization Good Clinical Practice (ICH GCP) and the following:

- United States (US) Code of Federal Regulations (CFR) applicable to clinical studies (45 CFR Part 46, 21 CFR Part 50, 21 CFR Part 56, 21 CFR Part 312, and/or 21 CFR Part 812)

Investigators and clinical trial staff who are responsible for the conduct, management, or oversight of the trial have completed Human Patients Protection and ICH GCP Training.

The protocol, informed consent form(s), recruitment materials, and all patient materials will be submitted to the Institutional Review Board (IRB) for review and approval. Approval of both the protocol and the consent form must be obtained before any patient is enrolled. Any amendment to the protocol will require review and approval by the IRB before the changes are implemented to the study. In addition, all changes to the consent form will be IRB-approved; a determination will be made regarding whether a new consent needs to be obtained from patients who provided consent, using a previously approved consent form.

1 PROTOCOL SUMMARY

1.1 SYNOPSIS

Title: **Bicuspid aortic valve replacement: Evaluation of transcatheter VERSus Surgery (BELIEVERS) Trial**

Study Description: The study is a multicenter, randomized superiority trial of **standard of care** therapies for **severe aortic stenosis** (AS) in patients with a bicuspid aortic valve (BAV). Namely, the therapies to which patients will be randomized will be **transcatheter** aortic valve replacement (TAVR) or **surgical** aortic valve replacement (SAVR), in patients deemed clinically suitable for both **following patient selection committee review**.

The null hypothesis is that there is **no difference between TAVR and SAVR** in relation to the hierarchical primary composite endpoint. The alternate hypothesis is that **TAVR differs from SAVR**. The test for superiority is two-sided, such that SAVR or TAVR superiority could be demonstrated.

Patients deemed suitable for randomization at the individual level by a local heart team will be **affirmed by the patient selection committee**. Patients deemed **unsuitable for randomization** but **meet inclusion criteria** and ultimately undergo SAVR or TAVR are of interest and will be entered into the SAVR and TAVR registry cohorts.

Objectives: The overarching goal of this study is to provide an evidence base for a structured and consistent image-guided precision-medicine based approach to guide patients and their providers to the most appropriate therapy for valve replacement for their particular BAV anatomy, weighing their "TAVR risk" (figure 1; predominantly driven by anatomical factors) with their "SAVR risk" (predominantly driven by clinical factors).

Endpoints:	Please see Table 1 below.
Study Population:	
Sample size: 1200 randomized patients required for 85% power to detect a difference (two-sided superiority).
 
Patients at 50 years of age or older at time of consent with severe aortic stenosis (AS) and a bicuspid aortic valve (BAV) deemed suitable for a bioprosthesis by a local heart team (unsuitable or patient declined a mechanical valve or Ross procedure, following demonstration of evidence-based shared decision making with a validated decision-aid(1)).

Description of Sites/Facilities Enrolling Patients:	At least 60 sites that perform both TAVR and SAVR are initially planned in the United States and Canada.
Description of Study Intervention:	
The study intervention is aortic valve replacement by TAVR or SAVR that are commercially available and standard of care devices. Patients will be randomized 1:1 to TAVR or SAVR using permuted block randomization with varying block size stratified by (1) sex and (2) low or intermediate/high SAVR (clinical) risk, (3) planned TAVR type (in the event of randomization to TAVR). Local heart team assessments of clinical risk assessment and anatomical risk assessment by CT corelab will be provided to the patient selection committee for final adjudication of TAVR and SAVR risk. For the patient to be suitable for randomization, there must be relative equipoise, defined as follows: the TAVR and SAVR risk strata, as per final adjudication by the patient selection committee based on site-reported (SAVR risk) and CT Corelab analyzed qualitative and quantitative data (TAVR risk), must not deviate by more than one risk stratum. For instance, a low SAVR risk patient cannot be randomized if the TAVR risk is deemed high, and vice versa. However, an intermediate SAVR risk patient could be randomized if the TAVR risk is low or high and vice versa. It is anticipated that the feasibility phase (around 20 sites) will enroll 10% of the full-scale study phase of 1200 randomized patients (1200 clinical trial patients from at least 60 and up to 80 sites).

Study Duration:	Estimated time from when the study opens to enrollment until completion of data analyses: 120 months. The current PCORI funding will cover the first 6.5 years, additional funding was secured for the remaining 3.5 years. Protocol will be revised as appropriate, at the end of the 6.5-year period, to reflect non-PCORI funding.
Patient Duration:	Time it will take for each individual patient to complete all patient visits: Follow-up is planned annually to 10 years. This will include standard of care clinic visit (in person or virtual) and a standard of care echocardiogram.

Table 1. Primary, Secondary, Safety and Exploratory Outcomes				
Primary or Secondary	Name of Outcome	Specific measure to be used	Timepoints	Estimated power (if applicable)
Primary	A hierarchical composite of: (1) death, (2) disabling stroke, (3) non-disabling stroke, (4) valve reintervention, (5) rehospitalization†, (6) unfavorable KCCQ (VARC-3*)	Hierarchical categorical using Win ratio (superiority)	Assessed at latest available annual follow-up (6y duration PCORI funded)	>85%
Key Secondary	Hierarchical composite of (1) death (2) time averaged KCCQ score.	Win ratio	Survival status assessed at latest available annual follow-up. KCCQ will be assessed as a time-average over patient follow-up	>95%
Secondary	Time averaged Kansas City Cardiomyopathy Questionnaire (KCCQ) status (continuous)	KCCQ questionnaire	Time average over all patient follow-up	>95%
Secondary	Kansas City Cardiomyopathy Questionnaire (KCCQ) status (continuous)	KCCQ questionnaire	From baseline to 1, 12, 24, 36, 48, 60, 72, 84, 96, 108, 120 months	Not powered
Secondary	CV rehospitalization days (count)	CRF: clinical events assessed by direct follow-up	Event driven	Not powered
Secondary	Short Form-12 (SF-12) Health Survey (continuous)	SF-12 questionnaire	From baseline to 1, 12, 24, 36, 48, 60, 72, 84, 96, 108, 120 months	Not powered
Secondary	New York Heart Association (NYHA) status (categorical)	NYHA clinical scale	From baseline to discharge, 1, 12, 24, 36, 48, 60, 72, 84, 96, 108, 120 months	Not powered
Secondary	6 min walk test (continuous)	6 min walk test distance	From baseline to 1, 12	Not powered
Secondary	Depression score (continuous)	PHQ-9 score	From baseline to 1, 12, 24, 36, 48, 60, 72, 84, 96, 108, 120 months	Not powered
Secondary	Time-to-recovery to baseline (categorical)	QOR-15 scale	From baseline to discharge, 1, 12 months	Not powered
Secondary	Death (time-to-event)	CRF: clinical events assessed by direct follow-up	Event driven	Not powered
Secondary	Cardiovascular death (time-to-event)	CRF: clinical events assessed by direct follow-up	Event driven	Not powered
Secondary	All stroke (time-to-first event) Ischemic, hemorrhagic, not otherwise specified	CRF: clinical events assessed by direct follow-up	Event driven	Not powered
Secondary	Disabling stroke (time-to-first event,)	CRF: clinical events assessed by direct follow-up	Event driven	Not powered
Secondary	Rehospitalization (valve-, procedure-, or HF-related); (time-to-first event)	CRF: clinical events assessed by direct follow-up	Event driven	Not powered
Secondary	Death/stroke/rehospitalization; (time-to-first event)	CRF: clinical events assessed by direct follow-up	Event driven	Not powered
Secondary	Aortic dissection (time-to-first event)	CRF: clinical events assessed by direct follow-up	Event driven	Not powered
Secondary	Need for surgery of the aorta (time-to-event)	CRF: clinical events assessed by direct follow-up	Event driven	Not powered

[figure not shown]
Secondary	Bioprosthetic valve failure (BVF); (time-to-first event)	Echo corelab determined	Event driven	Not powered
Secondary	Paravalvular leak severity (categorical)	Echo corelab determined	From baseline to discharge, 1, 12, 24, 36, 48, 60, 72, 84, 96, 108, 120 months	Not powered
Safety	Valve-related mortality (time-to-event)	CRF: clinical events assessed by direct follow-up	Event driven	Not powered
Safety	Myocardial infarction	CRF: clinical events assessed by direct follow-up	Event driven	Not powered
Safety	Coronary obstruction	CRF: clinical events assessed by direct follow-up	Event driven	Not powered
Safety	Major bleeding (VARC-3)	CRF: clinical events assessed by direct follow-up	Event driven	Not powered
Safety	Major vascular complication (VARC-3);	CRF: clinical events assessed by direct follow-up	Event driven	Not powered
Safety	Cardiac structural complication (major)	CRF: clinical events assessed by direct follow-up	Event driven	Not powered
Safety	Need for open heart surgery	CRF: clinical events assessed by direct follow-up	Event driven	Not powered
Safety	Atrial fibrillation/ atrial flutter	CRF: clinical events assessed by direct follow-up	Event driven	Not powered
Safety	Need for permanent pacemaker	CRF: clinical events assessed by direct follow-up	Event driven	Not powered
Safety	Device malpositioning (including embolization and migration)	CRF: clinical events assessed by direct follow-up	Event driven	Not powered
Safety	Acute Kidney Injury stage 3-4	CRF: clinical events assessed by direct follow-up	Event driven	Not powered
Safety	Endocarditis (valve-related)	CRF: clinical events assessed by direct follow-up	Event driven	Not powered
Safety	Clinically significant valve thrombosis (time-to-first event)	CRF: clinical events assessed by direct follow-up	Event driven	Not powered
Exploratory	Prosthesis-patient mismatch severity (categorical)	Echo corelab determined	From baseline to discharge, 1, 12, 24, 36, 48, 60, 72, 84, 96, 108, 120 months	Not powered
Exploratory	Subclinical valve thrombosis (time-to-first event)	CT corelab determined	Event driven	Not powered
Exploratory	Ascending aorta dimension > 50 mm (categorical)	CT corelab determined	From baseline to standard of care interval CTA	Not powered
Exploratory	Change in ascending aorta dimension from baseline to follow up as cm/y (continuous)	CT corelab determined	From baseline to standard of care interval CTA	Not powered

[figure not shown]
†valve or procedure related and including heart failure but excluding valve reintervention (CEC adjudicated)]

* <45 or a decrease of >10 from baseline as per VARC-3

Unless otherwise specified, definitions are based on VARC-3 (see appendix B).

Figure 1: Heart team assessment of TAVR vs SAVR risk

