1.2 SCHEMA

1.3 SCHEDULE OF ACTIVITIES

The majority of assessments and all laboratory and all non-invasive and invasive tests/interventions will follow the standard of care (SOC).

Visits	Screening and/or Baseline Day -90 to Day 0 (Before randomization)	procedure (valve implant – Day 0)	Post procedure (up to 72 hours post-procedure)	Discharge or 7 days post-procedure (whichever is c sooner)	30 days ±7 days	1 year ±30 days	Annual visits (2 to 10 year) ±45 days	Event Driven
Physical assessment								
Informed consent	X							
Demographics	X							
Medical history	X							
Physical exam (including height and weight)	X			X	X	X	X	
STS risk score	X							
EuroSCORE II	X							
SYNTAX score ¹	X							
Concomitant Medications	X			X	X	X	X	X ¹⁰
Adverse event assessment		X	X	X	X	X	X	X
NIHSS ²	X			X	X	X		X
mRS ²	X				X	X		X
Index Procedure		X						
Additional Cardiac Interventions								X
Hospitalizations			X					X
Laboratory measurements								
WBC, Hgb, Platelet Count	X		X	X	X	X		
Serum chemistry ³	X		X	X	X	X		
NT-ProBNP ⁴	X				X	X		
Pregnancy test ⁵	X							
Non-Invasive tests								
Vital signs	X		X	X	X	X	X	
12-Lead ECG/EKG	X		X	X	X	X	X ⁷	
Echocardiogram (TTE) ⁶	X		X		X	X	X	X
Pulmonary Function Test (PFT) ⁸	X							
Functional Assessments								
NYHA classification	X			X	X	X	X	
CCS angina	X							
6 min walk test	X				X	X		
Frailty index	X							
Quality-of-Life Assessments								
KCCQ	X				X	X	X	
SF-12	X				X	X	X	
QOR-15 scale (Quality of recovery)	X ¹²			X	X	X		
PHQ-9 scale (Depression score)	X				X	X	X	
Invasive tests								
3D Cardiac Contrast CT ⁹	X					X ¹⁰	X ¹⁰	X ¹⁰
Iliofemoral CT Angiography ⁹	X							
Invasive or CT coronary Angiography ⁹	X							
Supra-aortic angiogram or TEE (if performed)		X						
Final eligibility review								
Patient Selection Committee	X							
Randomization or assignment to registry	X							
Complete Case Report Forms (CRFs)	X	X	X	X	X	X	X	X

1. In the presence of coronary stenosis where coronary revascularization is deemed necessary.
2. NIHSS and mRS will be collected for all patients at screening/baseline as well as at the specified timepoints. In addition, during follow-up, NIHSS and mRS will be collected at the time of stroke and 30–90 days post-stroke only for patients who develop a new stroke during the trial.
3. Comprehensive metabolic panel (including but not limited to Albumin, total bilirubin, calcium, creatinine, glucose, potassium, AST, ALT, sodium, and eGFR).

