4. If the site does not have the capability to collect an NT-proBNP lab, a BNP lab can be collected instead.
5. Serum pregnancy test (only for women of childbearing potential).
6. Echocardiography can be done at any time post procedure before discharge
7. A 12-Lead ECG at 2-10 year follow-up will only be collected if done per standard of care.
8. Only for patients with history of severe lung disease.
9. A 3D cardiac imaging or Coronary Angiogram done within 1 year of the patient selection committee date can be used for screening. If a TEE or a cardiac MRI are available per standard of care within 6 month of the patient selection committee date, the images will be collected for the study.
10. 3D Cardiac Contrast CT will be performed following SOC as per ACC/AHA guidelines.
11. Selected medications.
12. It will be conducted at time of pre-procedure evaluation.

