- **Subclinical valve thrombosis (time-to-first event):** Imaging evidence of leaflet thrombosis (e.g., hypoattenuated leaflet thickening and/or reduced leaflet motion) with absent or mild hemodynamic changes and no symptoms or clinical sequelae.
- **Ascending aorta dimension >50 mm:** maximum ascending aorta diameter measured by CT Core Lab; endpoint met if >50 mm at any follow-up CT.
- **Change in ascending aorta dimension (cm/year):** annualized change in maximum ascending aorta diameter from baseline to follow-up CT by CT Core Lab.

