- **Representativeness of Patient Population.** From the outset, we will require that at least 35% of enrolled patients are women and at least 20% are from racial or ethnic minority groups. We have chosen initial sites that already treat a high proportion of these patients, and we are partnering with Heart Valve Voice and Heart Valve Surgery (patient advocacy organizations) to provide culturally tailored outreach material, multilingual e-consent, and community-oriented communication materials that will facilitate targeted recruitment. Enrollment metrics for sex and race will be periodically reviewed. If any site drifts more than five percentage points below either target for 3 consecutive months, the study team will deploy additional recruitment tools (e.g., transportation vouchers) and, if necessary, activate “reserve” sites whose historical case-mix exceeds the diversity thresholds. These steps will ensure that all key demographic subgroups reach the numbers required for ≥ 80 percent power in the planned interaction tests. Many per protocol questionnaires such as KCCQ are available in multiple languages and which will be used in the patients native tongue as necessary; some patient centered questionnaires (such as QOR) have not been translated or validated for languages other than English, in which case an interpreter will be used, if available at the treating center.
- Patients will be randomized 1:1 to TAVR or SAVR using permuted block randomization with varying block size. We will require **$\geq 35\%$ to be female**. To **ensure a balance between treatment arms**, randomization will be **stratified by (1) sex** and (2) low or intermediate/high SAVR (clinical) risk, (3) planned TAVR type (in the event of randomization to TAVR). Randomization will be adaptive to maintain balance in study arm allocation within each site. This study is open-label; patients, treating clinicians, and site staff will not be blinded to treatment assignment.
- All randomized patients will be assessed peri- and post-procedure, at discharge, 30 days, 1 year, and then annually for up to 10 years post-procedure. The visits at 30 days and 1 yr are to be in-person at investigational site. Visits at years 2 -10 can be virtual or in-person at investigational site. Labs, ECG and Echo may be done locally.

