9.4.8 Handling of missing data

The extent and pattern of missing data will be summarized by study arm and visit, including reasons for missingness when available.

For the Winratio analysis, participants without KCCQ at least 1-year post-randomization will have their KCCQ comparison considered as non-evaluable/tier, unless a higher-level component has already determined the winner.

For time-to-event endpoints, participants without an event will be right-censored at the last known contact date.

For longitudinal patient-reported and functional outcomes, models fitted by full maximum likelihood will be used, which provide valid inference under a missing-at-random (MAR) assumption conditional on included covariates and observed outcomes. As sensitivity analyses, departures from the MAR assumption will be assessed using delta-adjusted pattern-mixture models. Following multiple imputation under MAR, imputed outcome values occurring after permanent dropout will be systematically shifted by clinically meaningful offsets (δ) to reflect plausible worse (or better) unobserved outcomes. A range of δ values will be examined to evaluate robustness of conclusions.

For time-averaged KCCQ, missing KCCQ measurements will be imputed based on the the mean estimates from a linear mixed model with time as categorical covariate, study arm and the interaction between study arm and time as fixed effects and subject-specific random effects.

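### Subclinical valve thrombosis is read from standard-of-care CT, yet the stated censoring rule counts never-scanned patients as observed event-free to last contact

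*Protocol*

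**What the plan says.** The following statements in the protocol bear on this endpoint.

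- **Endpoint type and source.** Synopsis Table 1 lists "Subclinical valve thrombosis (time-to-first event") among the exploratory outcomes, with the measure "CT corelab determined", an event-driven timepoint and no power claim.
- **Definition.** Section 3, under the CT Core Lab endpoints: "Imaging evidence of leaflet thrombosis (e.g., hypoattenuated leaflet thickening and/or reduced leaflet motion) with absent or mild hemodynamic changes and no symptoms or clinical sequelae".
- **When CT is done.** Section 1.3 opens by saying that "all laboratory and all non-invasive and invasive tests/interventions will follow the standard of care (SOC"). The contrast-CT row is marked at 1 year, at the annual visits and in the event-driven column, each time with footnote 10: "3D Cardiac Contrast CT will be performed following SOC as per ACC/AHA guidelines". The visit lists in sections 8.6 and 8.7 contain no CT.
- **Censoring.** Section 9.4.8: "For time-to-event endpoints, participants without an event will be right-censored at the last known contact date". No exception is made for endpoints that need a scan.
- **Blinding.** Section 4.1: "This study is open-label; patients, treating clinicians, and site staff will not be blinded to treatment assignment".

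**The concern.** Right-censoring at last contact is valid when event status is known up to that contact. Death and stroke come to light through follow-up. A finding that causes no symptoms and at most mild hemodynamic change does not; it stays unknown until a CT is read. A patient who attends every visit for ten years and never has a CT contributes ten years recorded as event-free, although nobody has looked.

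Two things follow. The cumulative incidence is diluted by patients whose status was never assessed. And the hazard ratio between arms partly measures how often each arm is scanned. Clinicians who order the CTs know the assignment, and nothing in the protocol equalises CT use. A published TAVR-versus-SAVR contrast on leaflet thrombosis could then reflect scanning practice.

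**Working it through.** The protocol states no rate, power or CT frequency for this endpoint, so there is no figure to reproduce. The check is of the logic first, then an illustration on stated assumptions.

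**Logic.** (1) The event is established by a core-lab CT read. (2) Nothing clinical announces it; thrombosis with symptoms or sequelae is a separate safety endpoint. (3) No post-implant CT is required beyond standard of care. (4) Event-free participants stay at risk to last contact. Together these put never-scanned patients in the risk set as event-free. The other imaging endpoints are handled differently. In Table 1 the two aortic CT endpoints are tied to the standard-of-care CT itself, and the echo core-lab endpoints rest on echocardiograms scheduled through year 10.

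**Inputs for the illustration.** 600 patients per arm (section 9.4.1). The true cumulative incidence *p* (the same in both arms) and the share of each arm ever scanned *c* are assumptions. Scanning is taken as unrelated to thrombosis, and a scan is taken to detect it.

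**Formulas.** Detected proportion = *p* × *c*. Apparent hazard ratio = ln(1 − *p·c*₁) / ln(1 − *p·c*₂). The chance of a nominal difference is for a two-sided 5% comparison of two proportions.

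| True *p*, both arms | CT share, arm 1 / arm 2 | Events detected | Detected rate | Apparent HR | Chance of nominal significance |
|---|---|---|---|---|---|
| 10% | 30% / 30% | 18 / 18 | 3.0% / 3.0% | 1.00 | 5% |
| 10% | 35% / 25% | 21 / 15 | 3.5% / 2.5% | 1.41 | 17% |
| 10% | 40% / 20% | 24 / 12 | 4.0% / 2.0% | 2.02 | 53% |
| 10% | 60% / 20% | 36 / 12 | 6.0% / 2.0% | 3.06 | 94% |
| 20% | 30% / 30% | 36 / 36 | 6.0% / 6.0% | 1.00 | 5% |
| 20% | 40% / 20% | 48 / 24 | 8.0% / 4.0% | 2.04 | 83% |

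Worked line: 0.10 × 0.40 = 0.04 and 0.10 × 0.20 = 0.02; ln(0.96)/ln(0.98) = 2.02.

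With equal CT use the arm contrast is unbiased, but the absolute rate falls short by the unscanned share: 3% against 10% is 70% too low, and 1 − 0.30 = 0.70. With unequal use the apparent hazard ratio is close to the ratio of CT use. The recorded event date is also the scan date, not the onset, so the times are interval-censored.

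**Sensitivity to the scanning assumption.** Take *p* = 15% in both arms and CT in 50% versus 30%.

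- Scanning unrelated to thrombosis: the stated rule gives 0.15 × 0.50 = 7.5% and 0.15 × 0.30 = 4.5%, a ratio of 1.67. A scanned-only denominator gives 15% and 15%.
- Every case scanned: the stated rule gives 15% and 15%. A scanned-only denominator gives 15/50 = 30% and 15/30 = 50%, a ratio of 0.60.

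Neither denominator is safe under every scanning pattern.

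**The case against.** The strongest reply has four parts.

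- **The protocol fixes little here.** The censoring sentence is a general default. The time-to-event examples in section 9.4.3 do not name this endpoint, section 9.4.7 deals only with subgroups, and an SAP may refine the matter. This explains the gap but does not close it. The protocol fixes both the endpoint type and a rule for all time-to-event endpoints, and applied as written the rule gives a wrong rate. That is more than missing detail.
- **The stakes are low and the ascertainment is disclosed.** This stands. The endpoint is exploratory and unpowered, it lies outside the gatekeeping in section 9.4.4, and the reliance on standard-of-care CT is open.
- **The size is assumed.** This stands too. A reader might infer that the incidence is understated by exactly the unscanned share. That needs scanning to be unrelated to thrombosis. Mild hemodynamic change on a scheduled echocardiogram could prompt a CT, and scanning enriched for cases makes the shortfall smaller. A reader might also infer that CT is the only modality that could show the finding. The definition speaks of imaging evidence in general; CT is how Table 1 determines it.
- **A scanned-only denominator can itself mislead.** The 0.60 example shows this. The extreme behind it, with every case scanned, is implausible for an event without symptoms or sequelae and with at most mild hemodynamic change. A weaker selection by indication is quite possible, so the remedy needs a caveat.

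**Conclusion.** The point holds for this one exploratory endpoint. Under the stated rule, never-scanned patients count as observed event-free. The estimated incidence is therefore too low unless essentially every case is scanned, with a shortfall of up to the unscanned share if scanning is unrelated to thrombosis. If CT use differs between arms, the comparison is biased roughly in proportion to that difference.

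The actual size is unknown. The CT shares and true incidences in the table are assumptions. It would be tempting to conclude that the trial will show a spurious treatment effect. The documents do not support that: they contain no sign that CT use will differ by arm, and the open-label design only permits it. Nor does the problem reach the primary, key secondary or other confirmatory conclusions.

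**What to change.** Exempt subclinical valve thrombosis from the last-contact censoring rule in section 9.4.8, and state in Table 1 and the SAP that it is detected on standard-of-care CT. Then:

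- Report the proportion with leaflet thrombosis among patients with at least one core-lab-evaluable post-implant CT, accounting for time from procedure to CT. If a time-to-event display is kept, use interval-censored methods or censor at the last evaluable CT.
- Report the number, timing and indication of CTs by arm.
- Add a sensitivity analysis limited to CTs not prompted by suspected valve dysfunction.
- Present the comparison between arms as descriptive.

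The cost is wording and a CT-use table, plus recording the indication for each CT if that is not already collected. No scan is added. The downside is a smaller, selected denominator, which is itself unbiased only if scanning is unrelated to thrombosis within each arm. That condition should be stated beside the result.
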